6.3.3.3 Change from Baseline in Non-Convulsive Seizure Frequency

Algorithms for calculating mean non-convulsive seizure frequency and change from baseline will follow the same methods as described for the primary endpoint.

Change from baseline in non-convulsive seizures will be presented by seizure types (e.g., absence, myoclonic).

The statistical comparison of treatment group and placebo will be done using a nonparametric ANCOVA similar to the method described in 6.3.1.1. Here the analysis will use the ranks of the non-convulsive seizure frequencies as the response variable, treatment as a factor, and the ranks of the baseline non-convulsive seizure frequencies as a covariate. Data will be displayed by treatment group as described for the primary endpoint.

6.3.3.4 Change from Baseline in Convulsive Seizure Frequency by Seizure Type

Algorithms for calculating mean convulsive seizure frequency and change from baseline for each seizure type (GTC, tonic, clonic, hemiconvulsive, tonic-clonic, and focal seizures with an observable motor component) will follow the same methods as described for the primary endpoint.

Change from baseline in non-convulsive seizures will be presented for all non-convulsive seizures and by seizure types (e.g., focal, generalized).

The statistical comparison of treatment group and placebo will be done using a nonparametric ANCOVA similar to the method described in [6.3.1.1](#). Here the analysis will use the ranks of the non-convulsive seizure frequencies as the response variable, treatment as a factor, and the ranks of the baseline non-convulsive seizure frequencies as a covariate. Data will be displayed by treatment group as described for the primary endpoint.

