Table	14.2.1.10b	Percentage Change in Convulsive Seizure Frequency per 28 Days: Nonparametric Analysis – PP Population
Table	14.2.1.11b	Percentage Change in Convulsive Seizure Frequency per 28 Days by Baseline Convulsive Seizure Frequency (BCSF) Category: Parametric Analysis – mITT Population
	14.2.2	Efficacy – Proportion of subjects who achieve various % reductions in convulsive seizure frequency
Table	14.2.2.1.1b	Percent Reduction in Convulsive Seizure Frequency – mITT Population
Table	14.2.2.1.2b	Percent of Subjects Achieving Complete or Nearly Complete Convulsive Seizure Freedom – mITT Population
Figure	14.2.2.2b	Cumulative Response Curve for % Reduction in Seizure Frequency per 28 Days per 28 Days – mITT Population
Table	14.2.2.3b	Percent Reduction in Convulsive Seizure Frequency – PP Population
Figure	14.2.2.4b	Cumulative Response Curve for % Reduction in Convulsive Seizure Frequency per 28 Days - PP Population
Figure	14.2.2.5b	Cumulative Response Curve for % Subjects Experiencing Various % Reductions in Convulsive Seizure Frequency – All Subjects Increased and Decreased - mITT Population
	14.2.3	Efficacy – Longest interval between convulsive seizures
Table	14.2.3.1b	Duration of Longest Interval (Days) between Convulsive Seizures – mITT Population
Figure	14.2.3.2b	Boxplot of Duration of Longest Interval between Convulsive Seizures – mITT Population
Table	14.2.3.3b	Duration of Longest Interval (Days) between Convulsive Seizures – PP Population
	14.2.4	Efficacy – Number of convulsive seizure free days

Table	14.2.4.1b	Number of Convulsive Seizure Free Days per 28 Days: Parametric Analysis – mITT Population
Table	14.2.4.2b	Number of Convulsive Seizure Free Days per 28 Days: Nonparametric Analysis – mITT Population
	14.2.6	Efficacy – Change from baseline in non-convulsive and convulsive + non-convulsive seizure frequency
Table	14.2.6.1b	Change from Baseline in Non-Convulsive Seizure Frequency: Nonparametric Analysis – mITT Population
Table	14.2.6.2b	Change from Baseline in Non-Convulsive Seizure Frequency by Seizure Type: Nonparametric Analysis – mITT Population
Table	14.2.6.3b	Change from Baseline in Convulsive + Non-Convulsive Seizure Frequency: Nonparametric Analysis – mITT Population
Table	14.2.6.4b	Change from Baseline in Convulsive Seizure Frequency by Seizure Type: Nonparametric Analysis – mITT Population
	14.2.7	Efficacy – Incidence of rescue medication
Table	14.2.7.1b	Days with Rescue Medication Usage – mITT Population

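### SAP 6.3.3.4 is headed convulsive seizures by type, but its model sentence uses non-convulsive frequencies as response and covariate.

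*SAP*

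**What the plan says.** SAP 6.3.3.4 carries the heading "Change from Baseline in Convulsive Seizure Frequency by Seizure Type". It has three paragraphs.

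- **Paragraph 1** is about convulsive seizures. It opens "Algorithms for calculating mean convulsive seizure frequency and change from baseline for each seizure type", lists GTC, tonic, clonic, hemiconvulsive, tonic-clonic and focal motor seizures, and refers to the primary endpoint for the calculation.
- **Paragraph 2** is about non-convulsive seizures: "Change from baseline in non-convulsive seizures will be presented for all non-convulsive seizures and by seizure types".
- **Paragraph 3** specifies a rank ANCOVA. The response is given by "Here the analysis will use the ranks of the non-convulsive seizure frequencies as the response variable", treatment is the factor, and the covariate is "the ranks of the baseline non-convulsive seizure frequencies as a covariate".

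Appendix 1 lists the matching output as Table 14.2.6.4b: "Change from Baseline in Convulsive Seizure Frequency by Seizure Type: Nonparametric Analysis", for the mITT population. Non-convulsive seizures by type have a table of their own, 14.2.6.2b: "Change from Baseline in Non-Convulsive Seizure Frequency by Seizure Type: Nonparametric Analysis".

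**The concern.** A reader who goes to 6.3.3.4 for the treatment comparison on each convulsive type finds a derivation for convulsive seizures followed by a model for non-convulsive seizures. No sentence in the section gives a response or a baseline covariate for any convulsive type. Whoever produces Table 14.2.6.4b must either follow the text and fill the table with the wrong variable, or follow the title and depart from the written plan without a record of the change.

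At stake is a supportive result: which convulsive seizure types account for any treatment difference. The overall test of efficacy is not at stake.

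**Working it through.** No figure in the plan depends on this point, so there is nothing to compute. The check sets the relevant texts side by side.

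**Step 1. Compare 6.3.3.3 with 6.3.3.4.**

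| Element | SAP 6.3.3.3 | SAP 6.3.3.4 |
|---|---|---|
| Heading | Non-convulsive | Convulsive, by type |
| Frequency derived | Non-convulsive | Convulsive, six types |
| What is presented | Non-convulsive, by type | Non-convulsive, overall and by type |
| Response | "Here the analysis will use the ranks of the non-convulsive seizure frequencies as the response variable, treatment as a factor" | "Here the analysis will use the ranks of the non-convulsive seizure frequencies as the response variable" |
| Factor | Treatment | Treatment |
| Covariate | Ranks of baseline non-convulsive frequency | "the ranks of the baseline non-convulsive seizure frequencies as a covariate" |

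In 6.3.3.3 every row agrees with the heading. In 6.3.3.4 the first two rows are convulsive, and the presentation, response and covariate rows are non-convulsive. The model sentence is the same in both sections and fits only the first. Paragraph 2 of 6.3.3.4 is not an exact copy: its examples of types are focal and generalized, where 6.3.3.3 gives absence and myoclonic.

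**Step 2. Compare with the planned outputs.** Appendix 1 keeps the two by-type analyses apart, as Table 14.2.6.2b (non-convulsive) and Table 14.2.6.4b (convulsive). Section 6.3.3.3 already supplies the non-convulsive model. Section 6.3.3.4 is the only section that could supply the model for Table 14.2.6.4b, and it supplies one for the other seizure class.

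**Step 3. Look for a resolution elsewhere.** SAP 6.9, the list of changes from the protocol, does not mention the point. The analysis of combined seizures in 6.3.3.5 refers back to the non-convulsive method and gives nothing for convulsive types.

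**Step 4. Establish what remains specified.** Paragraph 1 of 6.3.3.4 refers to the primary-endpoint method in 6.3.1, which gives the frequency per 28 days, the difference and the percentage change. The table title fixes the endpoint, the population and a nonparametric approach. The gap is therefore the presentation sentence plus the response and covariate in the model sentence.

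**Step 5. Establish what depends on it.** SAP 6.1.2 confines formal testing to the primary endpoint and two key secondary endpoints, and this analysis is not among them. It is also not among the additional secondary objectives in SAP 2.3 or Protocol 2.3. Protocol 2.5.1 does list seizure counts by type as an efficacy endpoint, but specifies no test for them. No alpha allocation, power figure or sample size uses it.

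**The case against.** The best defence is that the intended variable can be recovered from the SAP itself. The heading, the first paragraph and the title of Table 14.2.6.4b all say convulsive, and the non-convulsive analysis has its own section and table. A competent programmer would be unlikely to fill a convulsive table with non-convulsive data. This stands as a limit on the consequence. It does not remove the error: the operative model sentence is wrong, and a correct guess would still be an unrecorded departure from a final SAP.

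Three stronger readings are tempting, and the documents do not support them.

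- A reader might infer that the six convulsive types would have no analysis at all. The derivation in paragraph 1 still supports descriptive results for each type; what lacks a correct specification is the treatment comparison.
- A reader might infer that the main support for the primary endpoint is lost. The SAP does not give this analysis that role. SAP 6.3.1.2 names the per-protocol and percentage-change analyses as supplementary, and rests the efficacy conclusion on the primary mITT analysis.
- A reader might infer that age group was also dropped by mistake and should be restored here. The model in 6.3.3.4 has treatment as its only factor, as do those in 6.3.3.3 and 6.3.3.6, and the rank ANCOVA text in 6.3.1.1 names no age term. Adding one would be a separate modelling proposal.

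**Conclusion.** The point holds as an internal inconsistency in one secondary analysis. As written, 6.3.3.4 repeats the 6.3.3.3 comparison, and the convulsive by-type treatment comparison has no correctly specified model. The per-type derivation and the output table are right. The primary and key secondary inferences, the error control and the sample size are unaffected. It is a minor correction, worth making because it is cheap and removes a choice that would otherwise be left to whoever produces the table.

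The conclusion rests on one reading: that the heading, paragraph 1 and Table 14.2.6.4b state the intent, and that the model sentence was carried over from 6.3.3.3. The identical sentence and the two separate by-type tables make that the natural reading.

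**What to change.** Change two paragraphs of SAP 6.3.3.4.

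- **Paragraph 2:** rewrite it to say that the change from baseline in convulsive seizures is presented for each convulsive seizure type. Drop the examples carried with the non-convulsive wording. Swapping a single word would leave a garbled sentence, so the paragraph needs rewriting.
- **Paragraph 3:** use ranks of the type-specific convulsive seizure frequency during T+M as the response, treatment as the factor, and ranks of the type-specific baseline convulsive frequency as the covariate. This matches Table 14.2.6.4b.

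Do not add age group as part of this correction. The cost is SAP wording only, with no new data, table or test. Making the change before unblinding would put it on record as a correction and not as a choice made with results in view.

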6.3.3.5 Change from Baseline in Convulsive + Non-Convulsive Seizure Frequency

The change from baseline in convulsive + non-convulsive seizure frequency will be calculated as described for the primary endpoint, but considering both convulsive and non-convulsive seizures.

The statistical comparison of treatment group and placebo will be performed using a nonparametric ANCOVA similar to that described above for the analysis of non-convulsive seizures. Data will be displayed by treatment group as described for the primary endpoint.

6.3.3.6 Incidence of Rescue Medication Usage

Use of rescue medication is recorded on the daily diary. In the event of prolonged seizures or status epilepticus, rescue medication is administered according to each subject's personalized regimen consisting of one or more medications. If the first rescue administration does not control the seizures, a second or even third round might be administered. The second and third round might use medications or doses different from the first round of rescue meds.

Rescue medication will be summarized by treatment group and by active treatment vs. Placebo for the following:

- The number of days rescue medication was taken (normalized to 28 days) will be summarized for the T + M period by the mean, standard deviation (SD), median and range. The ZX008 treatment group will be compared to the placebo group using a rank ANCOVA analogous to that described in [Section 6.3.1.1](#). Specifically, the ANCOVA will use ranks of rescue medication frequency during T+M as the response, and will incorporate treatment group as a classification factor and the ranks of rescue medication frequency during Baseline as a covariate.

6.3.3.7 Hospitalization and Other Resource Utilization to Treat Seizures

In order to better understand the healthcare resource burden associated with the management of Dravet syndrome, caregivers will be asked which of the following hospital and community-based healthcare services they had interactions with over the preceding month: emergency room services, ambulance, planned and unplanned hospitalization, family physician services, speech

and language therapy, occupational therapy, and physical therapy. This information will be captured in the CRF.

6.3.3.8 Incidence of Status Epilepticus

The incidence of status epilepticus will be evaluated based on cases captured as such with emergency treatment at treatment centers and entered as adverse events into the safety database, and also as convulsive seizures lasting longer than 10 min from the seizure diary. According to the International League Against Epilepsy definition, seizures over five minutes duration are to be considered SE.

The number and percentage of subjects with status epilepticus recorded as an AE will be presented by treatment group for the baseline and the T+M period per 28 days.

In addition, from the diary data, change from baseline in the number and percentage of convulsive seizures with duration >10 min for the baseline and T+M period will be reported. The number and percentage of subjects will be presented by treatment group for the baseline and the T+M period per 28 days.

All seizures recorded in the AE database as status epilepticus should also be included in the seizure diary. An edit check will be performed to identify the overlap between seizures related to hospitalization for SE and seizures entered into the diary as seizures > 10 min. (The definition of SE includes seizures lasting 5 min or longer, so not all SE will be recorded in the >10 min category.)

To ensure that all instances of SE are accounted for, a composite endpoint will be constructed that combines episodes of SE recorded as AEs with any other convulsive seizure with a duration > 10 min. The ZX008 and placebo groups will be compared on the composite endpoint using a Cochran-Mantel-Haenszel test with age group as stratification factor.

6.3.3.9 Duration of Prolonged Seizures

Duration of convulsive seizures at baseline and on treatment will be presented by treatment group using categories as <2 min, 2-10 min and >10 min.

To obtain a baseline probability distribution for the 3 categories, we will proceed as follows: For each subject, we will calculate the percentage of their total number of baseline seizures that is in each category. (For example, if the subject had 5 seizures, with 2 in the first category and 3 in the last category, their percentage distribution would be 40%, 0%, and 60% in the <2, 2-10, and >10 categories. We can calculate similar numbers for the next subject, and so on.) We will then average these over all subjects to obtain the % of subjects' seizures that were <2 min in duration, the % between 2-10 min in duration, and the % >10 min in duration. These 3 percentages should total 100%. Thus we will obtain a distribution of seizure duration for baseline.

Using the seizure duration data obtained for the T+M period, we will proceed similarly, to obtain a distribution for the T+M period.

It is expected that treatment with ZX008 will result in shorter duration of seizures (as well as fewer seizures) during T+M compared to placebo, i.e., the probability of longer seizures (>10 min) will be higher for the placebo group than for the ZX008 arms. This may be assessed by comparing the probability of a >10 min seizure during T+M to the same during baseline, for a treatment group, to the same for the Placebo group. It is expected that the ZX008 group will have greater odds of a reduction in proportion of seizures >10 min than the Placebo group. However, treatment with ZX008 may result in fewer seizures overall yet the duration of residual seizures may not be shorter. Should the primary or key secondary endpoints be positive for a given dose(s), but the duration of seizures not be shortened per above, exploratory evaluations may be undertaken to better understand the effect.

6.3.3.10 Quality of Life in Childhood Epilepsy (QOLCE) Scale

The parent/caregiver will complete this questionnaire for this assessment that looks at how epilepsy affects day-to-day functioning of their child in various life areas, including physical activities, well-being, cognition, social activities, behavior and general health, at baseline period (Visit 3), at Maintenance period (Visit 8) and at End of study (Visit 12). There is also one question on overall quality of life administered as part of the QOLCE.

The QOLCE scores items with a possible 5 point response. To calculate subscale scores, the 5 point item scores will first be reverse coded as necessary so that scores of 5 represent the best possible response and 1 represents the worst possible response. Item scores will then be transformed to a 0-100 scale as follows: 1-0, 2-25, 3-50, 4-75, 5-100. After transformation, a score for each subject for each subscale is calculated by averaging that subject's responses to each item in the subscale. The 16 subscale scores per subject are then averaged to obtain an overall quality of life score for each subject. The mean and SD across all subjects is then calculated for each subscale including the overall quality of life. The higher the subscale and overall quality of life scores, the better the response.

Table 2: Subscales of QOLCE:

Domain	Subscale	Item
Section 3: Physical	Physical Restrictions	3.1 a-j
Section 3: Physical	Energy/Fatigue	3.2 a,b
Section 4: Well-being	Depression	4.1 a,d,e,l
Section 4: Well-being	Anxiety	4.1 b,g,j,n,o,p
Section 4: Well-being	Control/helplessness	4.1 c,f,h,i
Section 4: Well-being	Self-esteem	4.1 k,m,q,r,s

Section 5: Cognition	Attention/Concentration	5.1 a,d,e,f,g
Section 5: Cognition	Memory	5.1 j,k,l,m,n,o
Section 5: Cognition	Language	5.1 p,q,r,s,t,u,v,w
Section 5: Cognition	Other Cognitive	5.1 b,c,h
Section 6: Social Activities	Social Interactions	6.1 c,f,h
Section 6: Social Activities	Social Activities	6.1. a,e, and 6.2
Section 6: Social Activities	Stigma Item	6.1 i
Section 7: Behavior	Behavior	7.1 a,c,f,g,h,i,j,k,l,m,o,q,r,s,t
Section 8: General Health	General Health	8.1
Section 2 (USA Version or Section 9 (Australia Version)	Quality of life item	2.1 or 9.1
	Overall Quality of Life	Average of the above 16 subscale scores

For each treatment group at Baseline and End of Study/ET, the mean (SD) score will be presented for each QOLCE subscale and for the overall quality of life score.

In addition, the change from baseline in each QOLCE subscale score will be calculated for each subject by subtracting the baseline score from the score measured at End of Study/ET. The change from baseline for each treatment group will be summarized by the mean (SD) and treatment groups will be compared using a Wilcoxon test.

Individual subject data for the domains will be listed.

